5.5 Study Evaluations

RCT participants will be asked to complete three brief surveys over a 6-month period. A small sub-set of participants will additionally be invited to participate in qualitative interviews.

Index Unmet Need Screen (survey #1): We will assess unmet needs among trial participants based on the index screen (administered prior to randomization). See **Appendix I** for the Index Unmet Need Survey.

Eight-Week Follow-Up Survey (survey #2): Eight weeks after the index screen, the RA will conduct phone follow-up with each Veteran to assess if they connected to any new resources in the intervening time and if so, to which one(s). See **Appendix J** for the Eight-Week Follow-Up Survey and accompanying phone script.

6-Month Unmet Need Re-Screen (survey #3): Six months after the index screen and by phone, the RA will re-administer the unmet need survey modified slightly

to exclude questions related to preferences for assistance (see **Appendix K** for the Six-Month Unmet Need Survey and accompanying phone script). We will define unmet need reduction in two ways: 1) one or more of baseline unmet needs no longer identified as an unmet need at the 6-month re-screen; and 2) percentage of baseline needs not reported as unmet needs at 6-month rescreen.

Qualitative Interviews with Veterans: Among study participants, we will purposefully select and recruit 60 Veterans to participate in qualitative interviews. The interviews are designed to understand the conditions that facilitate or impede a Veteran connecting to resources, as well as the conditions under which resources do or do not address a Veteran's needs. The RA at each study site will conduct the interviews. See **Appendix L and M** for the Veteran Interview Guides and accompanying phone scripts).

Qualitative Interviews with Representatives of VA and Community Resources: To understand how VA- and community-based programs experience the intervention, we will interview a purposeful sample of the VA- and community-based programs that trial participants used as a result of the intervention. The RA at each study site will conduct the interviews. See **Appendix N** for the Resource Representative Interview Guide and accompanying phone script.

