Statistical Power for Aim 1: With a sample of N=1760 Veterans completing the index unmet needs screening, we will have 80% power to detect small effect sizes ($f^2=.01$; $OR=1.47$) using 2-tailed significance tests at the $\alpha=.001$ level if the intraclass correlation coefficient (ICC) (for the nesting of patients within sites) is negligible, or medium effect sizes ($f^2=.15$; $OR=4.07$) even if the ICC is as high as .02 for testing associations between the presence of each unmet need and sociodemographic, adherence, utilization, and clinical (BP only) variables. HbA1c is anticipated to be a relevant clinical outcome for only 40% of the sample; for HbA1c, we will have 80% power to detect small effect sizes ($f^2=.03$; $OR=1.84$) using 2-tailed significance tests at the $\alpha=.001$ level if the ICC is negligible.

Statistical Power for Aim 2: The power analysis for Aim 2 focused on the primary outcome of connection to resources to address unmet needs. The sample size was determined based on previous research outside VA which found that individuals who completed a screening and referral intervention were 15% more likely (adjusted Odds Ratio (aOR)=2.1) to have enrolled in a new community resource to address unmet needs post-referral compared to patients in the non-intervention arm. In the present study, we will have 80% power to detect an effect of this size (aOR=2.1) across the three arms using 2-tailed significance tests at the $\alpha=.05$ level, even if we assume an attrition rate as high as 50% for the follow-up phone call at 8-weeks post-screen (retained N=440 across all sites and arms) and a conservative ICC value for patients nested within sites of .01. Previous empirical work found ICC values <.0001 when adjusting for a small number of covariates (e.g., race, marital status) to examine new connections to resources to address unmet needs; we intend to collect and use these covariates in the present study as well. Assuming an ICC value of .0001, we will have 80% power to detect an effect as small as an aOR=1.7 if we assume a 50% attrition rate for the 8-week follow-up phone call, or as small as an aOR=2.0 if we assume a 70% attrition rate. We based our attrition rate upon the study team's prior study where Veterans

had low incomes, high unemployment and low educational status, yet only 35% were lost to a follow-up interview.

Quantitative Data Analysis

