Our primary Aim 2 analysis will compare *connection to new resources* at 8-weeks post-index screen (our primary outcome of interest) across the study arms. HGLM will be used to control for the nesting of patients within sites. In all models, patient-level intercepts and slopes will be treated as random effects. We predict significantly greater connection to new resources in the ASSISTANCE arm

compared to the SCREENING arm, with the AWARENESS arm falling intermediate to these other two study arms.

Adherence, Utilization, and Clinical Outcomes. We will also conduct a series of secondary analyses to examine whether the study arms influence more distal outcomes, including adherence, utilization, and clinical outcomes. Specifically, to assess the impact of our intervention on more distal healthcare outcomes, we will use a difference-in-difference approach to examine whether changes from baseline at 6-months and 12-months post-referral differ across the three arms of our RCT (N=880). A series of HLM/HGLM analyses with patients nested within sites will examine differences in change from baseline across arms for the adherence, utilization, and clinical outcomes. As with the other analyses, all models will treat patient-level intercepts and predictors as random effects. We will have 80% power to detect small-to-medium effects ($f^2=.05$; OR=2.28) across the three arms using 2-tailed significance tests at the $\alpha=.05$ level, even if we assume a conservative ICC value for patients nested within sites of .01. HbA1c is anticipated to be a relevant clinical outcome for only 40% of the sample and we anticipate missing HbA1c test data for 17% of these Veterans in the year following their index screen; thus, for HbA1c, we will have 80% power to detect small-to-medium effects ($f^2=.08$; OR=2.71) across the three arms using 2-tailed significance tests at the $\alpha=.05$ level, even if we assume a conservative ICC value for patients nested within sites of .01.

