Unmet Need Reduction: Similar analyses will be used to examine differences across our three study arms in change from baseline in the proportion of unmet needs among the sub-sample of participants who complete the re-screening at 6-months post-referral. Among this sub-sample (N=220, assuming attrition rates of 50% at both the 8-week and 6-month follow-up phone surveys), we will have 80% power to detect a small-to-medium effect ($f^2=.09$; OR=2.94) across the three arms in terms of unmet need reduction using 2-tailed significance tests at the $\alpha=.05$ level, even if we assume a conservative ICC value for patients nested within sites of .01.

Differences in Intervention Effectiveness. In addition to examining how the S&R influences connection to new resources, we will conduct additional analyses to examine whether there is differential impact between the two referral arms (Awareness and Assistance) on connection to new unmet needs resources; unmet need reduction; and adherence, utilization and clinical outcomes among Veterans with certain unmet needs or with fewer unmet needs. While we predict that providing SW support (Assistance arm) will generally have a larger impact on outcomes than providing a Resource Sheet alone (Awareness arm), it would be beneficial to know if the Resource Sheet alone (or even the screening and

provision of generic list of resources) is sufficient to produce comparable changes in outcomes among Veterans with certain unmet needs or among Veterans with fewer unmet needs. If true, future implementation research could create tailored interventions that funnel the resources for more time- and cost-intensive referral strategies to only those Veterans who need it most.

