Appendix J: Eight-Week Follow-Up Survey

Phone Contact:

Hello, my name is _____, I'm calling from the (Name of VAMC). I am trying to reach [Name of Veteran].

Not Present: I'll call back another time, thank you. Is there a good time to try calling back?

Voicemail: Hello, my name is [name of research team member], I am calling from the (Name of VAMC). I wanted to speak with [Name of Veteran] about the Resource Needs Study. It's time to complete one of the brief questionnaires that are part of this study, it will only take about 5 minutes to complete. Please contact me at [name]. If you get my voicemail please leave your name, the best number to reach you at, and the most convenient times to reach you. Thank you.

Present: Hello, my names is [name of research team member] and I work at the (Name of VAMC). I wanted to speak with you about the Resource Needs Study you are participating in. It's time to complete one of the brief questionnaires that are part of this study, it will only take about 5 minutes to complete. Do you have a few minutes now?

If No: When is a good time for you to answer some questions about your social circumstances? (*SCHEDULE A TIME AND CONFIRM BEST CONTACT NUMBER*)

If Yes: Great, let's get started.

Screening Survey

1. Since we last talked on [insert index screening date], were you able to connect with any new programs or services for help with [insert needs identified from index screen)?

Yes

No (skip to Q5)

2. Which programs or services did you connect with?

3. Were you able to get the help you wanted from this (these) program(s)?

Yes

No

4. How did you connect with this (these) program(s)?

Probes

phone call

walk in

web-based

e-mail

5. Why were you unable to connect with the [insert specific resources that were provided to respondent at index screen, e.g., food, employment] programs(s)?

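### The primary model does not name the number of index needs as a covariate, although the any-need outcome probably depends on it; naming it is a modest, nearly free gain in power.

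*Combined protocol and SAP*

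**What the plan says.** **Outcome.** Question 1 of the eight-week survey (Appendix J) asks once per Veteran, "were you able to connect with any new programs or services for help with" the needs found at the index screen. One yes covers all of them.

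**Timing.** Section 5.5 says "We will assess unmet needs among trial participants based on the index screen (administered prior to randomization". Having at least one need is the entry condition for the trial, so the number of needs is available before the envelope is opened.

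**Primary model.** The Aim 2 primary analysis in Section 5.6 says "HGLM will be used to control for the nesting of patients within sites" and adds "In all models, patient-level intercepts and slopes will be treated as random effects". It names no patient-level predictor.

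**Covariates.** The Aim 2 power paragraph cites earlier work with a very small ICC "when adjusting for a small number of covariates (e.g., race, marital status") and continues: "we intend to collect and use these covariates in the present study as well". The list is given by example, and number of needs is not among the examples.

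**Where number of needs does appear.** Section 5.6 plans additional analyses of whether the two referral arms differ "among Veterans with certain unmet needs or with fewer unmet needs". That is a question about differential effect, not adjustment of the main comparison.

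**Need reduction.** Section 5.5 gives two definitions. The first is also of the any-need kind: "one or more of baseline unmet needs no longer identified as an unmet need at the 6-month re-screen". The second is a percentage of baseline needs.

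**The concern.** With an any-need outcome, a Veteran with four needs has four routes to a yes and a Veteran with one need has one. Unless extra needs make Veterans less able to follow up, the count should predict the outcome. A baseline predictor left out of the model costs some power, and chance imbalance in it goes uncorrected. Section 5.1 and Appendix A describe randomisation within site by envelopes opened in order of recruitment, with no stratification by number of needs, so the design does not balance it either.

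Two features make this worth a sentence in the plan. The planning effect is itself an adjusted odds ratio, so an adjusted model is already intended. And the covariate list is open, which leaves the content of the primary model to be settled later, possibly after outcomes are seen. At stake are a few points of power on a primary test that is planned at 80% after 50% loss to follow-up.

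**Working it through.** **1. Inputs from the plan (Section 5.6).** Odds ratio 2.1, described also as a 15% difference; two-sided alpha 0.05; 440 retained over three arms, so 440/3 ≈ 147 per arm; power 80%. The control rate is not given.

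**2. Control rate (assumption).** Read 15% as percentage points. With p1 = 0.2146, the odds are 0.2146/0.7854 = 0.2732; times 2.1 is 0.5738; p2 = 0.5738/1.5738 = 0.3646; difference 0.150. The other solution is 63.5% against 78.5%.

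**3. The plan's 80%.** One pair of arms, n = 147 each, no design effect because arms are compared within site:

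z = [d − 1.96·√(2p̄(1−p̄)/n)] / √([p1(1−p1) + p2(1−p2)]/n)

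With p̄ = 0.2896: √(0.4115/147) = 0.0529 and √(0.4002/147) = 0.0522, so z = (0.150 − 1.96 × 0.0529)/0.0522 ≈ 0.887 and power is 81.3%. Solving for 80% gives 143 per arm, or 429 in all, close to 440. The stated figure is reproduced on this reading.

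**4. Why the count should matter.** If each need has an independent chance q of a new connection, P(yes) = 1 − (1−q)^k for k needs. For illustration, q = 0.12 gives 12% for one need, 1 − 0.88² = 22.6% for two, 1 − 0.88³ = 31.9% for three and 1 − 0.88⁴ = 40.0% for four. The documents report no such association, so its strength has to be varied.

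**5. Simulation.** Logistic regression, 147 against 147, marginal odds ratio held at 2.1, with and without a linear term for number of needs, 4,000 to 6,000 runs per setting. The spread of needs is assumed (SD 1.0 to 2.2). Control rate 21.5%; unadjusted power 81% to 82%.

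| Assumed link between number of needs and connection | Change in power from adjusting (points) |
|---|---|
| None | −0.4 to +0.1 (simulation noise) |
| Odds ratio 1.15 per need | −0.1 to +0.7 |
| Odds ratio 1.3 per need | +0.7 to +2.6 |
| Odds ratio 1.5 per need | +1.4 to +5.5 |
| Odds ratio 2.0 per need | +4.4 to +12.9 |
| Odds ratio 0.77 per need (SD 1.64 only) | +1.2 |
| Each need has its own equal chance | +2.9 to +3.7 |

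With the own-chance structure and SD 1.64, the gain is larger at other control rates: +4.2 at 30%, +4.5 at 50% and +6.3 at 63.5%. A separate run of that structure with the coding 1, 2, 3, 4 or more (mean 2.4 needs, control about 21%) moved power from 81.4% to 85.9%.

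**6. In sample size.** By the formula in step 3, 85% power needs 163 per arm and 86% needs 168. Against 147, that is 16/147 = 11% to 21/147 = 14% more retained Veterans. As a rough cross-check, in the own-chance setting with SD 1.64 the count explains 8.4% of outcome variance among controls, and 147/(1 − 0.084) ≈ 160.

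**7. Need reduction.** At 220/3 ≈ 73 per arm and the plan's own odds ratio of 2.94, a pairwise test has about 82% to 90% power for control rates of 20% to 60%, before any adjustment. For the percentage definition, adding number of needs under the own-chance structure gave no gain: 69.1% to 67.8% in one setting and 78.4% to 77.5% in another, both within simulation noise.

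**The case against.** **The plan already adjusts.** A reader might infer that the plan rules out covariates. It does not. The power paragraph states an intention to use them, its list is by example, the target is an adjusted odds ratio, and the reference to patient-level slopes implies patient-level predictors. Supplemental models also control for earlier connection to resources. The accurate statement is that number of needs is not pre-specified. The gain beyond race and marital status was not estimated. Section 5.1 also mentions a separate Data Analysis Plan sent for monitoring-board approval; it is not among the documents reviewed and may list covariates.

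**The loss is not established.** A reader might infer that power is certainly being given away. The documents give neither the distribution of needs nor its link with connection. If there is no link, nothing is lost.

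**Need reduction.** A reader might infer that the six-month comparison is badly underpowered without this covariate. At the plan's own effect it is not (step 7); much lower power requires a smaller effect than the plan assumes. Section 5.6 analyses change in the proportion of needs, which is already scaled by the count. Only the any-need definition shares the structure of the primary outcome.

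**The count may be incomplete.** Section 5.1 lets participants decline any question, so some need items may be missing.

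**The estimand shifts.** The adjusted odds ratio is conditional on number of needs. In the simulations with SD 1.64 and an odds ratio of 1.15 to 1.5 per need, a marginal 2.1 became 2.12 to 2.27.

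All of these stand as limits. None gives a reason to leave the covariate unnamed.

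**Conclusion.** The point holds as a modest matter of efficiency and pre-specification. The randomised comparison without number of needs remains valid, and nothing here biases the primary test.

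The expected gain on the primary test is about 0 to 3 points of power if the association is weak (odds ratio up to 1.3 per need), and about 3 to 6 points if each need has its own chance of connection. Larger gains appear only with a very strong association and a wide spread of needs. In no setting did adjustment lower power beyond simulation noise.

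These sizes rest on four assumptions: 147 retained per arm, a marginal odds ratio of 2.1, an assumed distribution of needs, and comparison with a model that has no other covariate.

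**What to change.** In the Aim 2 primary analysis paragraph of Section 5.6, state that the primary HGLM for all three arms includes number of index needs (1, 2, 3, 4 or more) as a fixed covariate, alongside site and the covariates already intended, and close that list. Count needs by the rule used to decide eligibility, and say how a declined item is counted. Report the model without number of needs as a sensitivity analysis, and note that the primary odds ratio is conditional on the count.

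Do the same for any-need reduction (the first definition in Section 5.5) if it is modelled. The percentage definition does not need it.

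The cost is a few lines of text and no new data. Three extra parameters are easily carried by 440 Veterans: if the overall rate of yes lies between 21.5% and 36.5%, that is about 95 to 161 yes answers (440 × 0.215 and 440 × 0.365).

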- Our study will identify the full burden of unmet needs among Veterans as well as which needs and clusters of needs are most impactful with respect to outcomes, information that can inform how and where VA targets resources to address unmet needs.
- If our study finds that systematic screening and referral for unmet needs is associated with improved outcomes, our study will establish the needed evidence base for more wide-spread adoption of this practice, which has the chance to benefit all VA-enrolled Veterans who experience unmet social needs.

Safety and Data Monitoring Plan

Per FOA/RFA instructions, given that we are proposing a multisite intervention trial with human participants, HSR&D DSMB oversight is required. DSMB approval is accomplished by an independent review board chartered by HSR&D that meets at specified intervals and requires routine reporting from the PI. The PI will follow a specific Data and Safety Monitoring Plan and per HSR&D program guidelines, has submitted a Data Analysis Plan (DAP) as part of the Just-In-Time (JIT) compliance process. Studies are generally not allowed to begin until DSMB approval of the DAP has been provided. Currently, the DSMB meets on annual basis (generally in the early spring) but can request (or review) studies more frequently (if they determine that to be appropriate). The PI will receive a letter regarding the DSMB's determination after the meeting, including any concerns and follow-up actions; the PI will then submit these letters to VA CIRB.

We anticipate minimal risk, as the proposed intervention is survey-based and providing resources but once the study is underway, study staff and investigators will monitor any adverse events and immediately report any adverse events to the DSMB. The Principal Investigator (PI) and project manager (PM) will routinely audit the data for accuracy and make any necessary corrections to ensure data reliability and accuracy. In addition, the PI and PM will review the plans for and implementation of subject recruitment and enrollment, to ensure adequate recruitment progress and that recruitment milestones are met. Recruitment problems will be identified and addressed and if necessary, sites without adequate enrollment will be replaced.

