5.6 Data Analysis

Study Sample and Power Analysis

We aim for a total of 880 Veterans enrolled in the RCT (293/arm) based on power analyses provided below. Based on the study team's prior primary care-based studies with a similar recruitment approach, we anticipate 80% of patients approached to complete the index screen will participate. Based on pilot data from the Bedford MA VA where 78% of Veterans reported one or more needs, we then conservatively estimate that 50% of Veterans screened will report at least one of the nine unmet needs for which we will screen.

Thus, to yield a final sample of 880 Veterans with at least one unmet need enrolled in the study, we anticipate needing to approach 2200 eligible Veterans (733/site, or ~3 patients/day/site) i.e., of 2200, 80% (1760) will agree to participate in the study and of these, 50% (880) will have one or more unmet needs and be eligible for the RCT. If the participation rate or proportion of Veterans reporting at least one unmet need is lower than expected, we will increase the number of Veterans that we approach. We reviewed VA administrative data to determine the anticipated weekly count of Veterans eligible per site to participate in the study and there are more

than enough eligible Veterans to approach for additional screening if needed. We also anticipate drop-out rates at the 8-week follow-up survey to assess connection to resources and the 6-month unmet needs re-screen, respectively. Though the study team's prior study achieved a 65% follow up participation rate, here we conservatively anticipate a 50% participation rate for both the 8-week follow-up survey and the 6-month re-screen, reducing the sample for the three arms first to 440 Veterans total and then to 220 Veterans total.

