All data analysis will be conducted by study team members based in Boston. [name] is the study Data Analyst who will be responsible for developing the analytic data sets and all programming related to descriptive statistics and multivariate models. He will work closely with [name], the statistician who will be responsible for developing the statistical models and overseeing the overall analytic approach. All analysis will be conducted on VINCI.

Aim 1: Describe the prevalence and distribution of nine unmet needs (housing, food insecurity, utility insecurity, transportation, legal needs, employment, safety, social isolation, stress), and identify their associations with baseline sociodemographic characteristics, adherence, utilization and clinical outcomes.

Our primary analysis for Aim 1 will be descriptive. We will use data obtained during the index screening (N=1760) to generate descriptive statistics (e.g., proportions, 95% confidence intervals (CIs) to characterize the prevalence and distribution of each of the nine unmet needs at baseline across all study sites. We will next conduct inferential analyses to examine associations between unmet needs and sociodemographic characteristics as well as baseline outcomes (i.e., adherence, utilization, and clinical outcomes drawn from CDW data in the 12-months before the index screening for each Veteran). Hierarchical Linear Modeling will be used to control for the nesting of patients within sites, and patient-level variables will be treated as random effects. Hierarchical Generalized Linear Modeling (HGLM) will be used as appropriate to handle binary variables. Variables found to have statistically significant associations with unmet needs will be entered into multivariable models to better understand the correlates of each need. Bonferroni-corrected significance levels will control for multiple comparisons.

Aim 2: Compare the effectiveness of varying intensity referral strategies to address unmet needs on the primary outcome of connection to new resources to address unmet needs, and on secondary outcomes of post-intervention change in unmet needs, adherence, utilization, and clinical outcomes

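### The Aim 2 rule makes intercepts and slopes random with only three sites: fit arm and site as fixed effects for the primary outcome, or state that arm is already fixed

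*Combined protocol and SAP*

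**What the plan says.** The primary Aim 2 analysis (Section 5.6) compares connection to new resources at 8 weeks across the arms, using a hierarchical generalized linear model with patients nested in sites. The next sentence reads: "In all models, patient-level intercepts and slopes will be treated as random effects". For the adherence, utilization and clinical outcomes the wording becomes "all models will treat patient-level intercepts and predictors as random effects", and for Aim 1 it is "patient-level variables will be treated as random effects".

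Patients are recruited at three medical centers (Section 5.4). Section 5.1 and the Abstract randomize individual Veterans within each site, and Appendix A has envelopes opened participant by participant. Section 3.0 instead speaks of the site level; that phrase should be reconciled with the others. The within-site reading is used here.

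The power statement for Aim 2 claims 80% for an adjusted odds ratio of 2.1 with 440 retained and "a conservative ICC value for patients nested within sites of .01". It adds: "Assuming an ICC value of .0001, we will have 80% power to detect an effect as small as an aOR=1.7".

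No covariance structure, estimation method, degrees-of-freedom method or fallback for a singular fit is given. Section 5.1 notes that the PI "has submitted a Data Analysis Plan (DAP) as part of the Just-In-Time (JIT) compliance process"; that plan was not among the documents.

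**The concern.** With randomization inside sites, arm is a patient-level predictor, so a rule that makes all patient-level slopes random covers the two arm contrasts. Neither way of carrying it out is sound for the primary outcome.

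- **Slopes varying over sites.** The model needs a covariance matrix for the intercept and two arm slopes, estimated from three sites.
- **Slopes varying over patients.** Each Veteran gives one yes/no answer at 8 weeks (Appendix J, question 1). One binary observation per person cannot identify a personal intercept, still less a personal slope.

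At stake is the standard error of the primary comparison. A random arm slope can only widen it, by an amount that depends on choices the text leaves open, and the power calculation has no term for it.

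**Working it through.** **1. Rank.** Take the three site vectors (intercept, Awareness slope, Assistance slope) as deviations from their mean. The deviations sum to zero, so at most two are linearly independent and a 3 × 3 covariance estimated from them has rank at most 2. No assumed rate enters. In simulated logistic mixed fits with an unstructured matrix, the smallest eigenvalue was below 0.0001 in 600 of 600 trials in each of six settings, and effectively zero in 1,000 of 1,000 in a separate run. With a diagonal matrix, singularity is not certain, but at 440 analyzed and no true slope variance at least one of the three SDs was below 0.01 in 598 of 600 trials.

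**2. The plan's own power figure.** The control connection rate is not stated. Reading 15% more likely as 15 percentage points, together with an odds ratio of 2.1, gives 21.46% v 36.46% (assumption). With 440/3 = 146.67 per arm:

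- variance of the log odds ratio = 1/(146.67 × 0.2146 × 0.7854) + 1/(146.67 × 0.3646 × 0.6354) = 0.0405 + 0.0294 = 0.0699, so SE = 0.264
- ln 2.1 / 0.264 = 0.742 / 0.264 = 2.807
- power = Φ(2.807 − 1.960) = 80.1%

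This agrees with the stated 80% but does not reproduce it. It applies no ICC inflation, and the same method gives only 51% for an odds ratio of 1.7. Several of the plan's figures fit better with a regression F test, a design effect of 1 + (N/3 − 1) × ICC, and ln OR = 2f × π/√3. The numerator df are fitted here, not stated in the plan:

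| N | ICC | Numerator df | Detectable OR | Plan |
|---|---|---|---|---|
| 440 | .0001 | 2 | 1.72 | 1.7 |
| 264 (30% of 880) | .0001 | 2 | 2.01 | 2.0 |
| 292 (HbA1c: 880 × .40 × .83) | .01 | 3 | 2.71 | 2.71 |
| 220 | .01 | 3 | 2.94 | 2.94 |
| 440 | .01 | 1 or 2 | 2.15 or 2.34 | 2.1 |

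On either route site enters through an ICC at most, and nothing represents a random arm slope.

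**3. Illustration of the cost.** Assistance v Screening, equal sites, arm compared within site, two-sided 5%. With per-site variance s² = 3 × 0.0699 = 0.210, the fixed-arm SE is √(s²/3). With a random slope it is √((s² + τ̂²)/3), where τ̂² = max(0, SS/2 − s²) for REML or max(0, SS/3 − s²) for ML, and SS is the sum of squares of the three site log odds ratios about their mean. The logistic mixed fits are Laplace ML with a Wald z test, 600 trials per setting (error about 2 points), intercept ICC .01 and an assumed Awareness odds ratio of 1.45. N = 572 is 65% of 880, because the team's "prior study achieved a 65% follow up participation rate".

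| N | True slope SD (log odds) | Fixed arm | Random slope, z: REML / ML | Random slope, z: logistic fits, full / diagonal |
|---|---|---|---|---|
| 440 | 0 | 80% | 71% / 76% | 72% / 79% |
| 440 | 0.3 | 75–76% | 62% / 69% | 60% / 66% |
| 572 | 0 | 89–90% | 81% / 86% | 85% / 88% |
| 572 | 0.3 | 84% | 69% / 76% | 71% / 75% |

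A separate run of 1,000 logistic fits at N = 440 and SD 0 gave 80% fixed, 73% full and 78% diagonal. A REML-type approximation with an unstructured matrix came lower, at about 66%. The control rate matters: at 15% the N = 440, SD 0 figures are 71% fixed, 61% REML and 66% ML; at 30% they are 86%, 77% and 82%.

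**4. Price of fixed effects.** If the target were a wider population of sites with slope SD 0.3, the mean log odds ratio would have variance (0.210 + 0.09)/3, while the fixed-site test uses 0.210/3. Its effective critical value is 1.960 × √(0.210/0.300) = 1.64, so it rejects a zero mean effect about 10% of the time. At N = 572, s² = 0.210 × 440/572 = 0.161, the effective value is 1.57, and it rejects about 12%. Random-slope z tests reject about 7–9%. The slope SD of 0.3 is an assumption.

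**The case against.** **The sentence may not mean arm.** The phrase about patient-level intercepts and slopes is loose, and a power statement with only a site ICC fits a random site intercept with a fixed arm effect. On that reading the loss disappears. This stands as a possibility, and the Data Analysis Plan may confirm it. But the rule is given three times, once with slopes and once with predictors, so the text needs correcting either way.

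**The loss can be small.** This also stands. A diagonal covariance with a z test loses 1 or 2 points at 440, within simulation error. The 440 is the plan's deliberately cautious 50% follow-up, and at 65% the z tests stay above 80% when there is no slope variance. If the plan's claim for an odds ratio of 1.7 is taken at face value, z-test power at 2.1 is 93–96%.

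**Random slopes give some protection.** Appendix A has one social worker per site and local resource lists, so effects may differ by site, and the fixed-site test is the more anti-conservative for a wider population of sites. That is a real trade-off. But the random-slope z tests also exceed 5% there, because three sites cannot pin down the variance.

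**Stronger readings to avoid.** A reader might infer that the primary test has 56% or 35% power. Those are noncentral-t values on 4 and 2 df with site-by-arm variation as the error term. The documents name no df method, and the fitted mixed models referred to those critical values give different results (40–48% and 3–5%). A small-sample method would cut power much further, but no single figure can be attributed to this plan. A reader might also infer that the model cannot be run. A singular fit still returns a test.

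**Conclusion.** The random-effects rule is unsound for the primary analysis as written. On the site reading, the unstructured covariance cannot be full rank and the slope variance is not reliably estimable from three sites; on the patient reading, the effects are not identifiable. That part is algebra and does not depend on any assumed rate.

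The size is illustrative: about 80% power with a fixed arm effect against 71–79% with random arm slopes and a z test at N = 440, and 81–88% for the z test at N = 572. It rests on a 21.5% control rate, a pairwise contrast, equal sites and no true slope variance; true slope variance lowers it further. It does not show that the plan's 80% is wrong, nor that the trial is underpowered. Only the primary outcome was simulated. Confidence is moderate, because the wording is loose and the Data Analysis Plan was not available.

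**What to change.** - **Primary outcome.** Use logistic regression with arm (two indicators) and site (two indicators) as fixed effects, and no random arm slopes over three sites. Add a covariate list fixed before outcome data are seen. The power section names race and marital status only as examples, though it says "we intend to collect and use these covariates in the present study as well".
- **Site differences.** Report arm-by-site as a descriptive or sensitivity check.
- **Repeated secondary outcomes.** Keep a patient random intercept for the baseline, 6-month and 12-month measures, with site fixed.
- **If only a random site intercept was meant.** Replace the sentence with one saying that arm is fixed.
- **If the Data Analysis Plan already specifies the model.** Reconcile Section 5.6 with it, including covariance structure, estimator, df method and fallback, and restate power for that model.

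The cost is wording and a covariate list, with no change to data or sample size. The price is that inference is to these three sites, and any difference in effect between sites is not carried into the standard error. The SAP should say so.
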